### Document History – Changes compared to previous final version of SAP

Date	Time point	Reason for update	Outcome for update	Section and title impacted (Current)
25-01-2019	Prior to DB lock	Creation of final SAP	N/A - First version	NA
30-August-2022	Prior to DB lock	Protocol v05	Amendment 2.0	Section 1, 2

## List of abbreviations

AE	Adverse event
AESI	Adverse Event of Special Interest
ARR	Annualised Relapse Rate
CSR	Clinical Study report
DAR	Dose Administration Record
DMT	Disease Modifying Therapy
ECG	Electrocardiogram
EOS	End of Study
eCRF	Electronic Case Report Form
MedDRA	Medical Dictionary for Drug Regulatory Affairs
MS	Multiple Sclerosis
[REDACTED]	[REDACTED]
PK	Pharmacokinetics
[REDACTED]	[REDACTED]
RMS	Relapsing Multiple Sclerosis
SAE	Serious Adverse Event
SAP	Statistical Analysis Plan
SMQ	Standardized MedDRA Query
SOC	System Organ Class
TFLs	Tables, Figures, Listings
TSQM-9	Treatment Satisfaction Questionnaire for Medication
WHO	World Health Organization

## 1 Introduction

This document contains details of the statistical methods which will be used in the phase IIIb clinical trial CBAF312AUS02. The statistical analysis described in this SAP is based on the study protocol no. BAF312AUS02 Amendment Version 05 and will be presented in the Clinical Study Report (CSR). This document will also describe planned analysis for an interim analysis.

The purpose of this study is to assess early phase safety and tolerability of converting patients from approved oral, injectable or infusion RMS DMTs to siponimod. The results of this phase IIIb clinical trial CBAF312AUS02 will guide clinically relevant decisions related to the transition from frequently used RMS DMTs to siponimod and provide clinically relevant data on safety and tolerability for healthcare providers who are considering converting patients from currently approved RMS DMT to siponimod.

[figure not shown]
### 1.1 Study design

This is a 6-month, open-label, multi-center, single treatment arm design, including 300-400 advancing RMS patients, evaluating overall safety and tolerability profile when acutely converting to siponimod from oral, injectable or infusion RMS DMTs. This study consists of two parts: The Screening Period and Core Treatment Period.

- The patient cohort will be stratified by pre-treatment groups and may include injectable, oral or infusion DMTs used in RMS: interferon beta-1a (Avonex®, Rebif®), interferon beta-1b (Betaseron®, Extavia®), glatiramer acetate (Copaxone®, generic glatiramer acetate), peginterferon beta-1a (Plegridy®), teriflunomide (Aubagio®), fingolimod (Gilenya®, including generic forms of fingolimod), dimethyl fumarate (Tecfidera®, including generic forms of dimethyl fumarate, Vumerity® (diroximel fumarate)), natalizumab (Tysabri®), and ocrelizumab (Ocrevus®).
- Patients fulfilling the inclusion criteria, including genotyping, will undergo immediate conversion (please see below for exceptions) to siponimod, with “immediate” defined as cessation of the existing DMT and initiation of siponimod within 24 hours, followed by subsequent 5-day dose titration. Per inclusion criteria and screening phase testing requirements, fingolimod patients will undergo all required screening and/or Baseline testing, including genotyping for CYP2C9\*1\*1.
- Patients converting specifically from teriflunomide will undergo accelerated elimination prior to converting to siponimod over 11-14 days to allow for adequate drug elimination and minimize drug-drug interactions, in line with the Aubagio ® USPI.
- Patients converting from fingolimod will immediately convert to siponimod maintenance dose of 2mg, with no dose-titration.
- Patients treated with infusion DMT natalizumab (Tysabri®) will undergo at least a 4 week washout period at the time of consent, prior to converting to dose-titrated siponimod.
- Patients treated with infusion DMT ocrelizumab (Ocrevus®) will undergo at least 14 week washout period at the time of consent, prior to converting to dose-titrated siponimod.

- All patients initiating siponimod treatment, except those converting from fingolimod, will be titrated over 5 days to achieve a maintenance dose of 2mg by Day 6 with the following schedule of siponimod:

Figure 1: EXCHANGE study design

[figure not shown]
\*Injectable DMTs: interferon beta-1a, interferon beta-1b, glatiramer acetate, peginterferon beta-1a  
\*\*Teriflunomide strata will undergo accelerated elimination over 11-14 days per product USPI  
DMT: disease modifying therapy. EoS: End of Study  
Novartis Data on File: BAF312A/Siponimod – Clinical Trial Protocol CBAF312AUS02

Approximately 300-400 patients will be enrolled in this study from up to 80 study sites in the USA. The study plans to screen approximately 570 patients.

Since this is a single arm open-label trial, randomization is not being considered.

The primary aim of this study is to evaluate the overall safety and tolerability profile of siponimod 2 mg in patients with relapsing forms of MS who are converting from existing oral, injectable or infusion DMTs. The primary analysis will be performed at Visit 5 i.e. End of Study.

An interim analyses on the safety data will be conducted at the time of approximately 50 patients complete their Visit 5 (Day 168).

## 1.2 Study objectives and endpoints

Objectives	Endpoints
Primary	
The primary objective is to evaluate overall safety and tolerability profile of siponimod in advancing RMS patients who are converting from currently approved oral, injectable or infusion RMS DMT.	Occurrence of any study-drug related adverse events during 6-month treatment period
Secondary	
To evaluate treatment satisfaction with siponimod in advancing RMS patients using outcomes based on the Treatment Satisfaction Questionnaire for Medication (TSQM-9).	Change from Baseline in the TSQM-9
To evaluate cardiac safety during siponimod treatment initiation	

• Change from Baseline in heart rate to 6 hours after 1st treatment

• Occurrence of any adverse Events

• Occurrence of hospitalizations

To evaluate treatment persistence with siponimod	

• Patient retention

## 2 Statistical methods

This section contains information that will be used to draft CSR Section 9.7 on statistical analysis.

### 2.1 Data analysis general information

All data will be analyzed by Novartis using the statistical software SAS version 9.4 or higher according to the data analysis Section 12 of the study protocol, which is available in Appendix 16.1.1 of the CSR. Important information is given in the following sections and details are provided, as applicable, in Appendix 16.1.9 of the CSR.

In general, for continuous data, number of observations, mean, standard deviation, minimum, 25th percentile, median, 75th percentile, and maximum will be presented. Categorical data will be presented as frequencies and percentages.

#### 2.1.1 General definitions

##### 2.1.1.1 Study treatment

The investigational drug siponimod is formulated in film coated tablet, which contains 0.25mg, 0.5mg, 1.0mg and 2.0mg siponimod as siponimod fumaric co-crystal (active ingredient).

All eligible patients in the core treatment period will start the treatment with a 5-day dose titration pack continuing to a maintenance dose of 2.0 mg.

Patients on fingolimod enrolled on / after Amendment 3 of the protocol, will directly start with the maintenance dose. Therefore, patients on fingolimod will have 2 groups:

1. Fingolimod with titration dose (patients enrolled in the Protocol versions 0, 1 and 2)
2. Fingolimod with direct maintenance dose (patients enrolled in Amendment 3 or after).

**Figure 2 Siponimod Target Daily Dose**

Treatment Schedule for All Pre-treatment groups (including Fingolimod under Protocol Version 0,1 and 2):	
Titration Dose	
Day of Treatment	Target Dose
1	0.25 mg
2	0.25 mg
3	0.5 mg
4	0.75 mg
5	1.25 mg
Maintenance Dose	
Day of Treatment	Target Dose
6 and beyond	2 mg

Treatment Schedule for Fingolimod Patients (enrolled in Amendment 3 or after):	
Maintenance Dose Only	
Day of Treatment	Target Dose
1 and beyond	2 mg

### 2.1.1.2 Study day

Study day is defined with respect to the first day on which treatment with Siponimod starts. The date of first administration of study medication is defined as Day 1 and the day before is defined as Day -1.

Therefore, for any particular date, study day will be calculated as follows:

- For dates on or after the first date of study medication administration,  
Study day = Assessment date – Date of first administration of study medication + 1;
- For dates prior to the first date of study medication administration,  
Study day = Assessment date – Date of first administration of study medication.

### 2.1.1.3 Baseline definition

Baseline visit (Visit 1) is defined as the day on which patients start with their first dose of Siponimod.

Baseline is defined as the last measurement on or prior to Baseline visit.

#### Post-Baseline assessments

Post-Baseline values are defined as assessments taken after the start of study treatment.

When change from Baseline is of interest, the following formula will be for each scheduled visit and time-point where Baseline and post-Baseline values are both available:

Change from Baseline = Post-Baseline value – Baseline value.

### 2.1.1.4 Visit Window

*Visit-windows* will be used for the data that is summarized by visit; they are based on the study evaluation schedule and comprise a set of days around the nominal visit day. For any assessment, there are the protocol defined scheduled visits around which visit windows were created to cover the complete range of days within the study. The visit windows are shown in [Table 1](#). These apply to measurements taken at every visit. For assessments collected less often different visit windows will be applied as detailed below.

When visit windows are used, all visits will be re-aligned, i.e., they will be mapped into one of the visit windows. E.g., if the *Week 4* visit of a patient is delayed and occurs on Day 46 instead of on Day 29, say, it will be re-aligned to visit window *Week 8*. In the case of major deviations from the visit schedule, or due to unscheduled visits, several assessments of a patient may fall

in a particular visit window (either scheduled or unscheduled). Statistical approaches to handle multiple assessments in a given visit window are specified below.

Of note, patients are allowed to have gaps in visits.

**Table 1 Assessment windows for scheduled visits**

Visit Name	Days	Scheduled Day of Visit	Visit Window
Screening	-28 Days	-28	-28 days to Day 1*
Baseline (Visit 1)	Day 1	1	Day 1 - 4
Visit 2	Day 7	7	Day 5 - 18
Visit 3	Day 28	28	Day 19 - 56
Visit 4	Day 84	84	Day 57 - 126
Visit 5/EOS	Day 168	168	Day 127 - 183
Follow up visits	Follow up visits	198	Day 184 - 205

Day 1\*: refers to the day 1 before dose administration.

For parameters which are not collected at every visit, visit windows defined in Table 1 will be combined. For example, if a parameter is measured at Day 28 and Day 84 only, Day 28 visit window will extend from Day 5 to Day 56 (combining Day 7 to Day 28 visit windows). If more than one assessment falls into the interval, the rules defined in [Section 2.1.1.5](#) below are applied.

### 2.1.1.5 Multiple assessments within visit windows

When there are *multiple assessments* in a particular visit window, the following rules are applied to select one value “representing” the patient in summary statistics in a visit window (See **Table 1** ).

For Baseline assessment, definition see [Section 2.1.1.3](#). For post-Baseline visit windows the following applies (unless otherwise specified):

- For *quantitative variables*, the *closest* to the actual visit is chosen (if two assessments have the same distance, then the earlier one will be chosen);
- For *qualitative variables*, the *worst* record is selected. It is noted that in the analyses performed, *worst* case is always well defined.

In case qualitative variables are based on quantitative variables, the visit will be assigned to the quantitative variable, and this visit will be used for the derived qualitative variable.

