- During all other study visits, outside of Day 1 (screening, V2, V3, V4 and V5) a qualified study personnel, as determined by the PI, will assess the patient's heart rate.
- Patients will then follow the normal visit schedule in the treatment period and should complete all of the relevant assessments as indicated in Table 8-1.

Patients should have all visits/assessments as outlined in the Assessment schedule Table 8-1 or as close to the designated day/time as possible with an allowed visit window of ± 3 days for visit 1 (BSL), an allowed visit window of ± 5 days for visits 2, 3, 4, 5 and an allowed ± 7 days for the 30-day telephone follow-up. Missed or rescheduled visits should not lead to automatic

Patients who prematurely discontinue the study for any reason should be scheduled for a visit as soon as possible, at which time all of the assessments listed for the final visit will be performed. At this final visit, all dispensed investigational product should be reconciled, and the adverse event and concomitant medications recorded on the eCRF.

End of Treatment/Study (EOT/S) Visit Schedule

discontinuation.

For patients who complete the core treatment period of the study, the end of treatment/study visit should be conducted. No study drug should be taken on the day of EOT/S.

For patients who discontinue study medication prematurely in the core treatment period, the end of treatment/study visit should be conducted when they stop taking study medication.

A follow-up telephone call, 30 days after the end of treatment/study visit, will be conducted for all patients who randomize.

As per Section 4.6, during a Public Health emergency as declared by Local or Regional authorities i.e. pandemic, epidemic or natural disaster that limits or prevents on-site study visits, alternative methods of providing continuing care may be implemented by the investigator as the situation dictates. If allowable by a local Health Authority and depending on operational capabilities, phone calls, virtual contacts (e.g. tele consult) or visits by site staff/ home nursing staff to the participant's home, can replace on-site study visits, for the duration of the disruption until it is safe for the participant to visit the site again.

Table 8-1 Assessment Schedule

Period	Scree	ening	Treatment			End of Treatment/St udy	Follow-up	Unplanned
Visit	Screening	Baseline ¹	Titration Treatment Period			End of Treatment/St udy	Safety	Unscheduled Visit

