8.5 Additional assessments

8.5.1 Clinical Outcome Assessments (COAs)

Patient reported outcomes (PRO)

The following PROs will be assessed in this study. These questionnaires will be administered to patients per scheduled visits listed in the schedule of assessments.

[figure not shown]
• Treatment Satisfaction Questionnaire for Medical (TSQM-9)

While all screening assessments are expected to be conducted on-site, the option for home health nursing may be utilized to replace on-site study visits for the remainder of the trial. In this case, home health nurses will provide technology to complete COAs.

Trial Feedback

At Visit 1 (baseline), Visit 4 (Day 84), and Visit 5 (Day 168/EOT/S), patients might be asked to complete an optional anonymized questionnaire, "Trial Feedback Questionnaire" to provide feedback on their clinical trial experience. Responses would be used to understand where improvements can be made in the clinical trial process. This questionnaire is not meant to collect data about the patient's disease, symptoms or adverse events and therefore would not be considered to be trial data. Should any spontaneous information be collected about AEs, it would be transferred to the safety database. Patients may opt in or opt out of completing this questionnaire. The data will be used to help understand and conduct clinical trials better in the future.

As per Section 4.6, during a Public Health emergency as declared by Local or Regional authorities i.e. pandemic, epidemic or natural disaster, that limits or prevents on-site study visits, COA data may be collected remotely.

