### **2.6.3 Handling of missing values/censoring/discontinuations**

No missing data will be imputed.

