***If Item 9 is missing***

$([\text{Sum (Item 7 and Item 8)} - 2] \text{ divided by } 8) * 100$

It should be noted that only one item may be missing from each scale before the subscale should be considered invalid for that respondent.

Change in TSQM-9 from Baseline with respect to domain scores to each post-Baseline time point will be summarized by providing: number of observations, mean, standard deviation, minimum, 25th percentile, median, 75th percentile, and maximum.

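### SAP windowing discards many early stoppers' exit TSQM-9 scores, and no exit before Day 127 counts at Visit 5; add an end-of-treatment summary

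*SAP*

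**What the plan says.** **Collection.** For a patient who stops drug early, Protocol Section 8 says "the end of treatment/study visit should be conducted when they stop taking study medication". A patient who leaves the study prematurely is likewise seen as soon as possible, "at which time all of the assessments listed for the final visit will be performed". Table 8-1 marks TSQM-9 at V1, V3, V4 and Exit/V5, so an exit score is expected. Protocol 8.5.1 ties the questionnaire to that table: "These questionnaires will be administered to patients per scheduled visits listed in the schedule of assessments".

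**Windows.** SAP 2.1.1.4 re-aligns visits by study day. Table 1 gives Visit 2 as Day 5-18, Visit 3 as Day 19-56, Visit 4 as Day 57-126 and Visit 5/EOS as Day 127-183. For a parameter not collected at Visit 2, which is the case for TSQM-9, windows are merged: "Day 28 visit window will extend from Day 5 to Day 56 (combining Day 7 to Day 28 visit windows").

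**Selection.** When a post-Baseline window holds several quantitative values, SAP 2.1.1.5 keeps the closest one: "to the actual visit is chosen (if two assessments have the same distance, then the earlier one will be chosen").

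**Summary.** SAP 2.10 states: "Change in TSQM-9 from Baseline with respect to domain scores to each post-Baseline time point will be summarized by providing" the usual descriptive statistics. SAP 2.6.3 adds "No missing data will be imputed", and SAP 2.5.4 plans no sensitivity or supportive analysis. No end-of-treatment or last-on-treatment TSQM-9 summary is defined.

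**The concern.** The protocol goes to some trouble to obtain a last rating from patients who stop. The SAP then treats that rating as a rival to the scheduled score in the same window, and the scheduled score usually wins. Nothing later in the SAP brings the exit rating back.

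TSQM-9 is the measure for one of the three secondary objectives, satisfaction with siponimod. SAP 2.10 itself describes the instrument as predictive of adherence, which makes it plausible that patients who stop score lower. The study has one arm and is meant to inform switching decisions. A reader will probably take the Visit 5 figure as satisfaction after switching, when it describes only those still on drug to about Day 127 or later.

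Elsewhere the SAP does provide for such visits: the any-time section for notable vital signs (SAP 2.7.9.1.2) explicitly uses premature discontinuation visits. TSQM-9 has no counterpart.

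**Working it through.** **Inputs.** TSQM-9 schedule: Protocol Table 8-1 (Days 1, 28, 84, 168). Windows: SAP Table 1. Selection rule: SAP 2.1.1.5, reading the actual visit as the scheduled day. Visit tolerance: Protocol Section 8, "an allowed visit window of ± 5 days for visits 2, 3, 4, 5". The earliest on-time Visit 5 is Day 168 - 5 = 163, so an early exit is one on or before Day 162.

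**The plan's own figure.** Joining Visit 2 (Day 5-18) to Visit 3 (Day 19-56) gives Day 5-56, which matches the SAP's example.

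**Fate of the exit score, with Visit 3 on Day 28 and Visit 4 on Day 84:**

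| Exit day | What happens | Days |
|---|---|---|
| 2-4 | In the Baseline window but after the Baseline value; unused | 3 |
| 5-28 | Shown at Visit 3 | 24 |
| 29-56 | Discarded; Day 28 is closer | 28 |
| 57-84 | Shown at Visit 4 | 28 |
| 85-126 | Discarded; Day 84 is closer | 42 |
| 127-162 | Counted at Visit 5 | 36 |

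From Day 5 to Day 162 there are 162 - 5 + 1 = 158 days.

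- Discarded: 28 + 42 = 70; 70/158 = 44%.
- Shown at an earlier visit: 24 + 28 = 52; 52/158 = 33%.
- Counted at Visit 5: 36/158 = 23%.
- Exits on Days 5-126 only: 70/122 = 57% discarded, none at Visit 5.

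**Visits off schedule.** With Visits 3 and 4 five days early (Days 23 and 79), exits on Days 33-56 and 89-126 are discarded: 24 + 38 = 62 days. Five days late (Days 33 and 89), the discarded exits are Days 34-56 and 90-126: 23 + 37 = 60 days. The tie-break decides only single days, such as Day 33 against a Visit 3 on Day 23.

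**Timing of exits (assumed).** A simulation with visits varying by up to 5 days and exits over Days 2-162 gave 41% discarded, 2% unused in the Baseline window, 35% at Visit 3 or 4 and 22% at Visit 5 when exits were uniform. With exits concentrated early (half-lives of 30-90 days) it gave 32-39% discarded and 3-13% at Visit 5.

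**Number of scores (assumed 10-25% early discontinuation, uniform exits).** Unused = N × rate × (0.407 + 0.019).

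- N = 300: 300 × 0.10 × 0.426 = 13 to 300 × 0.25 × 0.426 = 32.
- N = 400: 400 × 0.10 × 0.426 = 17 to 400 × 0.25 × 0.426 = 43.

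**Possible shift in the mean.** If a share p is left out of Visit 5 and rates g points lower, then mean of those included - mean of all = p × g. With p = 10-20% and g = 15-30 on the 0-100 scale (both assumed), 0.10 × 15 = 1.5 and 0.20 × 30 = 6. This measures absence from Visit 5, whatever its cause. It does not measure the effect of the discard rule.

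**The case against.** The strongest reply is that a by-visit summary is entitled to be by-visit. A score from Day 30 or Day 100 is not a Day 168 score, so leaving it out of Visit 5 is ordinary windowing. Calling the Day 168 mean too high presumes a target, the last rating over all treated patients, that neither document states. The proposed row would mix a few days of exposure with 24 weeks. The endpoint is descriptive, with no hypothesis and no key secondary analysis. The number of observations, retention and reasons for discontinuation are all reported. A patient whose exit score is discarded because a scheduled score is closer still contributes that scheduled score. All of this stands. It argues for leaving the by-visit tables alone, but not against showing ratings already collected.

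A reader might go further in four ways that the documents do not support.

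- *That Visit 5 contains only patients who stayed on drug throughout.* Exits on Days 127-162 fall in the Visit 5 window and count.
- *That every early exit score is lost.* Exits on Days 5-28 and 57-84 are kept, under Visit 3 or Visit 4.
- *That the tie-break is the cause.* The loss comes from keeping the closest value together with Table 1. Absence from Visit 5 comes from Table 1, no imputation and the lack of an end-of-treatment summary; changing 2.1.1.5 alone would not alter it.
- *That the bias is known to be 1.5-6 points.* Both inputs are assumed. Patients who withdraw consent have no further assessments (Protocol 9.1.2), and those lost to follow-up give no exit score, so the range is an upper one.

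The SAP wording is also not clean. *Actual visit* could mean the scheduled day or the date attended; the two agree when visits are on schedule. The example in SAP 2.1.1.4 sends Day 46 to a Week 8 window, whereas Table 1 has no such window and places Day 46 in Visit 3. The exact discard days assume that Table 1 governs.

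**Conclusion.** The concern holds in limited form. As the SAP is written, a collected exit TSQM-9 is discarded when a scheduled score in the same window lies closer to the scheduled day. That covers 70 of 158 possible early-exit days (44%) with visits on schedule, and about 32-41% of early exits under the simulated timing patterns. No exit before Day 127 counts at Visit 5.

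The Visit 5 summary is a valid description of patients who stayed on drug to about Day 127 or later. It is not a description of satisfaction among all who switched. If stoppers rate lower it will look more favourable than a summary that includes them. The direction is plausible, but the amount cannot be derived from the documents. This is a worthwhile, inexpensive improvement to a descriptive secondary endpoint and does not touch the primary analysis.

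**What to change.** In SAP 2.10, add a supplementary end-of-treatment summary for each TSQM-9 domain. Define it as change from Baseline to the last post-Baseline TSQM-9, including the premature exit visit, and exempt it from the one-value-per-window rule in 2.1.1.5, which already allows exceptions where specified. Show it beside the observed Day 168 summary and by completed/discontinued status. Leave the by-visit summaries and the no-imputation rule as they are; the new row uses observed values only.

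In the same edit, state in 2.1.1.5 whether closeness is measured to the scheduled day, and reconcile the Day 46 example in 2.1.1.4 with Table 1.

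The cost is a sentence or two of SAP text and one extra row per domain, with the split by status, from data the protocol already collects. The row mixes durations of exposure, so it should be labelled supplementary, and it may look less favourable than the Day 168 figure. It cannot recover patients who gave no exit score.
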